#### **10.6.3.2 Analysis of Secondary Efficacy Endpoints**

- Percent change from baseline at the primary analysis time point in fasting LDL-C will be compared between each ISIS 681257 treatment groups and pooled placebo group using an ANCOVA model with baseline as covariate
- Proportion of patients who achieve  $\leq 50$  mg/dL in fasting Lp(a) at the primary analysis time point will be compared between each ISIS 681257 treatment group and pooled placebo group using a logistic regression model with Baseline Lp(a) as a covariate. Proportion of patients who achieve  $\leq 30$  mg/dL in fasting Lp(a) at the primary analysis time point will be analyzed similarly
- Percent change from baseline at the primary analysis time point in fasting apoB, OxPL-apo(a) and OxPL-apoB will be compared between ISIS 681257 treatment groups and pooled placebo group using an ANCOVA model with baseline as covariate

All analyses of secondary endpoints will be performed on the FAS as primary and PPS as supportive.

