Study Design	This is a multicenter, randomized, double-blind, placebo-controlled, dose-ranging study. Approximately 270 patients will be randomized in a 5:1 ratio to receive ISIS 681257 or placebo. This number was chosen to provide statistical power for both efficacy and safety assessments. Study Drug (ISIS 681257 or placebo) will be administered SC every week, every 2 weeks, or every 4 weeks, depending on cohort assignment, for up to 52 weekly doses, up to 26 every 2-week doses, or up to 13 every 4-week doses. Minimum treatment duration is 6 months. Maximum treatment duration is 12 months.  The treatment portion of the study will be complete when the last enrolled patient reaches 6 months of exposure. All patients will then enter a 16-week post-treatment follow-up period.  The primary efficacy and safety analysis time point is at Week 25 for patients who received every 4-week dosing (Cohorts A-C) and at Week 27 for patients who received every 2-week or weekly dosing (Cohorts D and E, respectively). For patients continuing treatment beyond the primary analysis time point additional supportive efficacy and safety analyses will be repeated at the completion of Study Drug treatment.  An independent Data and Safety Monitoring Board (DSMB) will be established to review safety, tolerability and efficacy (as needed) data collected on ISIS 681257 during this study, both individual events and aggregate data.
Number of Subjects	Approximately 270
Study Population	Inclusion Criteria  1. Must have given written informed consent (signed and dated) and any authorizations required by local law and be able to comply with all study requirements  2. Males or females aged $\geq 18$ and $\leq 80$ years old at the time of informed consent  3. Clinical diagnosis of CVD defined as documented coronary artery disease, stroke, or peripheral artery disease  4. Lp(a) plasma level $\geq 60$ mg/dL  5. Must be on standard-of-care preventative therapy for other than elevated Lp(a) CVD risk factors

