#### **2.4 Rationale for Dose and Schedule of Administration**

The Phase 1 program evaluated ISIS 681257 doses of 10 mg, 20 mg, and 40 mg given weekly that were found to be generally well-tolerated and to induce clinically-relevant reductions in Lp(a).

The range of dosing proposed for the present study will provide the equivalent drug exposure of 5 mg, 10 mg, 15 mg, and 20 mg administered weekly, and is predicted (based on modelling of PK/PD data obtained in Phase 1 study) to result in mean reductions from baseline in plasma Lp(a) ranging from approximately 60% to 85% at steady-state.

The highest dose selected for this study, 20 mg per week, is predicted to provide an approximately 85% reduction in Lp(a) at steady-state that is expected to be sufficient to bring almost all patients with hyperlipoproteinemia(a) into the normal range ( $Lp(a) \leq 30$  mg/dL).

The present study will also evaluate safety and efficacy at different dosing frequencies: every 4 weeks, every 2 weeks, and weekly. Patients with hyperlipoproteinemia(a) will require chronic treatment and thus every 2 weeks or every 4 weeks dosing regimens, if safe and well-tolerated, may provide advantages over weekly dosing in terms of convenience and compliance for patients. Dosing regimens of 20 mg every 2 weeks and 40 mg every 4 weeks will test if similar monthly exposure, at different frequencies of administration, will achieve similar safety and similar level of Lp(a) reduction since the reduction achieved by a given dose level is principally

driven by total exposure, while individual dose levels and the related peak concentration ( $C_{\max}$ ) may influence tolerance and safety.

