### 3. EXPERIMENTAL PLAN

#### 3.1 Study Design

This is a Phase 2, multicenter, randomized, double-blind, placebo-controlled, dose-ranging study. Approximately 270 patients will be randomized in a 5:1 ratio (225 ISIS 681257 and 45 placebo) to receive ISIS 681257 or placebo. Study Drug (ISIS 681257 or placebo) will be administered SC every week, every 2 weeks (biweekly), or every 4 weeks, depending on cohort assignment, for up to 52 weekly doses, up to 26 every 2-week doses, or up to 13 every-4-week doses.

The primary analysis time point is at Week 25 for patients who received every 4-week dosing (Cohorts A-C) and at Week 27 for patients who received 2-week or weekly dosing (Cohorts D and E). For patients continuing treatment beyond the primary analysis time point additional supportive efficacy analysis (to evaluate whether the treatment effect is maintained) and safety analysis (for the purpose of dose(s) selection) will be repeated at the completion of Study Drug treatment.

The treatment portion of the study will be complete when the last enrolled patient reaches 6 months of exposure. All patients will then enter a 16-week post-treatment follow-up period.

Patients  $\geq 18$  and  $\leq 80$  years old with elevated plasma Lp(a) levels ( $\geq 60$  mg/dL ) and a clinical diagnosis of CVD are eligible for enrollment upon meeting the study specific eligibility criteria. Patients will be on standard-of-care preventative therapy for other than elevated Lp(a) CVD risk factors as per current guidelines.

Clinical diagnosis of CVD is defined as documented coronary artery disease (CAD), stroke, or peripheral artery disease (PAD). A diagnosis of CAD has to be documented by any of the following:

- Angiographic evidence of  $\geq 50\%$  stenosis of 1 or more major epicardial coronary arteries
- History of myocardial infarction documented by positive enzymes, and either symptoms of myocardial ischemia, or ECG changes ([Thygesen et al. 2012](#))
- History of coronary revascularization
- Evidence of cardiac ischemia on exercise testing, or imaging study

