### **10.2 Sample Size Considerations**

Based upon prior clinical trial experience with ISIS 681257, it is estimated that the standard deviation of the percent change in Lp(a) is approximately 20%. With 23 patients in each ISIS 681257 treatment group and 23 in placebo group there would be approximately 90% power to detect a 20% difference in percent change in Lp(a) levels between the ISIS 681257 treatment groups and placebo group at an alpha level of 0.05, assuming 30% reduction in the ISIS 681257 patients and 10% reduction in the placebo patients.

Based upon prior clinical trial experience with Ionis ASOs, assuming the incidence rate of platelet count below lower limit of normal (LLN) in placebo treated patients is 1.9%, in the ISIS 681257 treated patients is 3.8%, twice the incidence rate observed in placebo, with 45 patients in each ISIS 681257 treatment group, there would be approximately 80% power to detect at least 1 event.

Therefore, approximately 270 patients (54 patients per cohort, including 45 patients per cohort treated with ISIS 681257) will be randomized to ensure that both the safety and efficacy of ISIS 681257 will be adequately characterized in the study.

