#### **10.6 Planned Methods of Analysis**

Summary tabulations will be provided for disposition, demographic, baseline, efficacy, and safety data as noted in the following sections. Hypothesis testing will be used for the primary efficacy endpoint and select secondary efficacy endpoints.

All eCRF data, lab data transfers, and any outcomes derived from the data will be provided in the patient data listings. Patient data listings will be presented for all patients enrolled into the study. Descriptive summary statistics including n, mean, median, standard deviation, standard error, interquartile range (25th percentile, 75th percentile), and range (minimum, maximum) for continuous variables, and counts and percentages for categorical variables will be used to summarize most data. Where appropriate, p-values will be reported. All statistical tests will be conducted using 2-sided tests with 5% Type I error rate unless otherwise stated.

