### **10.6.3.2 Analysis of Secondary Efficacy Endpoints**

- Percent change from baseline at the primary analysis time point in fasting LDL-C will be compared between each ISIS 681257 treatment groups and pooled placebo group using an ANCOVA model with baseline as covariate
- Proportion of patients who achieve  $\leq 50$  mg/dL in fasting Lp(a) at the primary analysis time point will be compared between each ISIS 681257 treatment group and pooled placebo group using a logistic regression model with Baseline Lp(a) as a covariate. Proportion of patients who achieve  $\leq 30$  mg/dL in fasting Lp(a) at the primary analysis time point will be analyzed similarly

- Percent change from baseline at the primary analysis time point in fasting apoB, OxPL-apo(a) and OxPL-apoB will be compared between ISIS 681257 treatment groups and pooled placebo group using an ANCOVA model with baseline as covariate

All analyses of secondary endpoints will be performed on the FAS as primary and PPS as supportive.

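### The logistic regression prescribed for the threshold endpoints is likely to separate at 30 mg/dL, leaving no usable odds ratio; a penalised or exact method should be named

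*Protocol*

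**What the plan says.** Protocol section 10.6.3.2 (Amendment 4) states that the proportion reaching 50 mg/dL or less "will be compared between each ISIS 681257 treatment group and pooled placebo group using a logistic regression model with Baseline Lp(a) as a covariate". The proportion reaching 30 mg/dL or less "in fasting Lp(a) at the primary analysis time point will be analyzed similarly". The same model sentence stands in the Amendment 3 text in the file. Neither version names an estimator, a test statistic, or a method for empty cells. Section 10.6 adds: "All statistical tests will be conducted using 2-sided tests with 5% Type I error rate unless otherwise stated".

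Four other statements bear on how many patients will respond:

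- **Entry.** Inclusion criterion 4 requires Lp(a) of at least 60 mg/dL.
- **Size.** Section 3.1: "Approximately 270 patients will be randomized in a 5:1 ratio (225 ISIS 681257 and 45 placebo". That is 45 pooled placebo patients and 45 in each of five active groups.
- **Planning figures.** Section 10.2 takes an SD of the percent change of about 20%, "assuming 30% reduction in the ISIS 681257 patients and 10% reduction in the placebo patients".
- **Predicted effect.** Section 2.4 predicts mean reductions of about 60% to 85% across regimens. The 85% at the highest dose is "expected to be sufficient to bring almost all patients with hyperlipoproteinemia(a) into the normal range", meaning 30 mg/dL or less. Section 2.1.1 describes untreated Lp(a) as generally stable within a person.

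**The concern.** The protocol expects few or no placebo patients, and many active patients, to reach 30 mg/dL. If no placebo patient responds, the treatment indicator separates the data. The likelihood then keeps rising as the treatment coefficient grows, and the maximum-likelihood odds ratio has no finite value. Because placebo is pooled, one empty cell affects all five dose comparisons at once. Two of the six secondary endpoints use this model, and the odds ratio is the effect measure it delivers for comparing each dose with placebo. The failure can be foreseen from the protocol's own statements, so the remedy can be written down before any data are seen.

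**Working it through.** **Reproducing the stated power.** Section 10.2 gives about 90% for 23 versus 23, a difference of 20 points, SD 20 and two-sided alpha 0.05. The noncentrality is 20 / (20 × √(2/23)) = 3.39, and the two-sample t-test power is 91.2%. The figure reproduces. No power or expected responder rate is stated for the threshold endpoints.

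**Chance of no placebo responder at 30 mg/dL.** For a placebo patient with baseline b, mean reduction m and standard deviation SD (both in percentage points), p = Φ([m − 100(1 − 30/b)] / SD). For 45 patients, P(none) = (1 − p)^45.

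With the planning figures m = 10, SD = 20:

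- All baselines 60 (fall of 50% needed): p = Φ(−2) = 2.3%, P(none) = 36%.
- All baselines 75 (60% needed): p = Φ(−2.5) = 0.62%, P(none) = 76%.
- All baselines 100 (70% needed): p = Φ(−3) = 0.13%, P(none) = 94%.

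The protocol does not give the baseline distribution. I assumed 60 plus an exponential excess with mean 15 to 60 mg/dL (median baseline about 70 to 102) and averaged p over it:

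| Placebo mean change, SD | p at 30 | P(none of 45) |
|---|---|---|
| −10%, 20% (planning figures) | 0.98% to 0.39% | 64% to 84% |
| 0, 20% | 0.24% to 0.09% | 90% to 96% |
| 0, 15% | about 0.01% or less | at least 99.5% |

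With mean change 0 and SD 20, if every patient sat exactly at 60, p = Φ(−2.5) and P(none) = 76%. The SD of 15% is an assumption; the protocol gives only 20%.

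**What separation does to the fit.** Take 43/45 active versus 0/45 placebo. Ordinary maximum likelihood with the baseline covariate does not converge: the log odds ratio drifts to about 33 to 39, the standard error exceeds 400,000 and the Wald p-value is about 0.9999. The likelihood-ratio p-value from the same model is about 3 × 10⁻²⁵, and Fisher's exact p is about 2 × 10⁻²³. The risk difference is 43/45 − 0 = 95.6 points and is perfectly well defined.

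**Simulation at 30 mg/dL.** I ran 400 trials of 45 versus 45 per scenario. The mean baseline excess was 20 or 40. The active mean reduction was 60% (SD 20) or 85% (SD 10). Placebo was −10%/20%, 0/20% or 0/10%. The Wald test rejected in 0% to 34% of trials overall, and in none of the trials without a placebo responder. The likelihood-ratio, Firth penalised likelihood-ratio and Fisher tests rejected in 100%.

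**At 50 mg/dL.** A fall of only 16.7% is needed from a baseline of 60. Over the same assumed baselines, the planning figures give placebo response rates of 7% to 18% and P(none) of about 0% to 4%. An empty placebo cell is therefore not the likely route. With an active mean reduction of 60% and the planning placebo figures, the Wald test rejected in at least 98% of trials.

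Separation can instead come from all 45 active patients responding. At an 85% reduction with an assumed SD of 10, this happened in 48% to 93% of simulated trials (mean excess 40 and 20). Wald power was 1% to 40%, with the other three tests at 100%. If the protocol's SD of 20 also applied to that dose, the same formula gives active response rates of 94.1% and 98.1%. The chance that all 45 respond is then 0.941^45 ≈ 6% and 0.981^45 ≈ 43%.

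**The case against.** The best defence is that the protocol says only logistic regression. It mentions neither maximum likelihood nor a Wald test, and Firth and exact methods are logistic regressions with the same covariate. Section 10 leaves software and additional methods to a separate SAP, which is not among the documents and may already deal with empty cells. The likelihood-ratio test of the same model loses nothing. Section 10.6 also promises counts and percentages, so a result such as 43/45 versus 0/45 would be plain to see, and dose selection in section 10.1.4 does not turn on these p-values.

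Most of this stands, and it rules out three stronger readings.

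- **That placebo responders at 30 mg/dL will almost certainly be zero.** The planning figures do not give that. They give 64% to 84%, and 36% if every patient sat at the entry floor. Near-certainty needs a stable placebo with a smaller SD. Section 2.1.1 supports stability but puts no number on it.
- **That the plan will miss a near-total effect.** That is true only of a Wald test, which the protocol does not name.
- **That the method would have to change after unblinding.** An unseen SAP could prevent that.

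The defence does not rescue the estimate. An unqualified logistic regression would normally be fitted by maximum likelihood. A likelihood-ratio test repairs the p-value but leaves the odds ratio infinite.

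**Conclusion.** The point holds as a cheap and worthwhile improvement: it should be fixed, but it is not critical. At 30 mg/dL separation is more likely than not across the assumed baseline distributions, though not if all baselines lay at 60 under the planning figures. The range depends on that baseline assumption and on normally distributed percent changes. At 50 mg/dL an empty placebo cell is not expected. Separation there is mainly a matter of the highest dose and depends heavily on the assumed baseline and active SD. What would be lost is the effect estimate for one, and possibly two, secondary endpoints. The p-value would be lost as well only if a Wald test were used. The primary ANCOVA and its sensitivity analyses are untouched.

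**What to change.** In section 10.6.3.2, or in the SAP with the protocol sentence aligned to it, state for both threshold endpoints that each active group is compared with pooled placebo by Firth penalised-likelihood logistic regression with baseline Lp(a) as covariate. The confidence interval and p-value should come from the penalised profile likelihood. Exact logistic regression is an acceptable alternative. Also report the risk difference versus pooled placebo with a Newcombe or Miettinen-Nurminen 95% confidence interval, which stays interpretable when a cell is empty or full.

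The cost is one or two sentences and standard software options. The one drawback is that penalised odds ratios are slightly shrunken. Sample size and data collection do not change.

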#### **10.6.4 Pharmacokinetic and Immunogenicity Analysis**

For all patients, trough and post-treatment concentrations of ISIS 681257 in plasma (as total full length oligonucleotides, including fully conjugated, partially conjugated, and unconjugated ISIS 681257) will be determined and summarized by treatment with stratification by subject immunogenicity status using descriptive statistics.

In addition, non-compartmental PK analysis of ISIS 681257 concentrations will be carried out on each individual patient data set in patients who received ISIS 681257 treatment, and the plasma disposition half-life ( $t_{1/2\lambda_z}$ ) associated with the apparent terminal elimination phase will be calculated, if appropriate, using available data at the End-of-Treatment and the post-treatment follow-up period from the equation,  $t_{1/2\lambda_z} = 0.693/\lambda_z$ , where  $\lambda_z$  is the rate constant associated with the apparent terminal elimination phase.

For patients in the PK subgroup only, non-compartmental PK analysis of ISIS 681257 will be carried out on each individual patient data set in patients who received ISIS 681257 treatment. The maximum observed drug concentration ( $C_{max}$ ) and the time taken to reach  $C_{max}$  ( $T_{max}$ ) will be obtained directly from the concentration-time data. Following single dosing (Day 1), area under the plasma concentration-time curve from time zero (pre-dose) to 24 hours after the dose ( $AUC_{0-24hr}$ ) will be calculated using the linear trapezoidal rule. Following multiple dosing,  $AUC_{0-24hr}$  and area under the plasma concentration-time curve during the time of each sampled dosing interval ( $\tau$ ) at steady-state ( $AUC_{\tau}$ ) will be calculated using the linear trapezoidal rule.

Other PK parameters, as appropriate, may be determined or calculated at the discretion of the PK scientist. Plasma PK parameters will be summarized using descriptive statistics with stratification by subject immunogenicity status. Exposure-response relationships between selected PD [e.g.,  $Lp(a)$ ] and PK measures (including but may not be limited to plasma trough concentrations) may be explored (including with and without stratification by IM status) in this study, or in a separate population PK analysis with all clinical studies combined.

The immunogenicity (IM) of ISIS 681257 will be assessed before, during, and after treatment with Study Drug (ISIS 681257 or placebo). The IM incidence (number) and incidence rate (percent) will be summarized at each evaluated study time point and at the patient level by treatment and dose, as the total number of and percent of evaluated patients with antibody negative, positive, and unknown status. Study patients with positive anti-ISIS 681257 antibody status may be further classified (when applicable) as being either 'persistent', 'transient', or not determinable. Potential relationships of immunogenicity with selected efficacy, safety, and PK measures may be evaluated.

Additional details regarding the PK and immunogenicity analysis will be described in the SAP.

## **11. INVESTIGATOR'S REGULATORY OBLIGATIONS**

### **11.1 Informed Consent**

The written informed consent document should be prepared in the language(s) of the potential patient population, based on an English version provided by the Sponsor or designee.

Before a patient's participation in the trial, the Investigator is responsible for obtaining written informed consent from the patient or legally acceptable representative after adequate explanation of the aims, methods, anticipated benefits, and potential hazards of the study and before any protocol-specific screening procedures or any Study Drug ISIS 681257 or placebo) are administered.

Importantly, patients should be informed of the possibility and risks of a reduction in platelet count and other potential risks, in particular hepatic and renal risks, and the importance of strict adherence to the monitoring program. The patient or legally acceptable representative must be given sufficient time to consider whether to participate in the study.

The acquisition of informed consent and the patient's agreement or refusal to notify his/her primary care physician should be documented in the patient's medical records and the informed consent form should be signed and personally dated by the patient or a legally acceptable representative and by the person who conducted the informed consent discussion (not necessarily an Investigator). The original signed informed consent form should be retained in the Study Master File and in any other locations required by institutional policy, and a copy of the signed consent form should be provided to the patient or legally acceptable representative.

## **11.2 Ethical Conduct of the Study**

The Guidelines of the World Medical Association (WMA) Declaration of Helsinki dated October 2013 the applicable regulations and guidelines of current Good Clinical Practice (GCP) as well as the demands of national drug and data protection laws and other applicable regulatory requirements will be strictly followed.

## **11.3 Independent Ethics Committee (IEC)/Institutional Review Board (IRB)**

A copy of the protocol, proposed informed consent forms, other written patient information, and any proposed advertising material must be submitted to the IEC/IRB for written approval. A copy of the written approval of the protocol and informed consent form must be received by the Sponsor or designee before recruitment of patients into the study and shipment of Study Drug. A copy of the written approval of any other items/materials that must be approved by the Study Center or IEC/IRB must also be received by the Sponsor or designee before recruitment of patients into the study and shipment of Study Drug. The Investigator's Brochure must be submitted to the IEC/IRB for acknowledgement.

The Investigator must submit to and, where necessary, obtain approval from the IEC/IRB, for all subsequent protocol amendments and changes to the informed consent document. The Investigator should also notify the IEC/IRB of SAEs occurring at the Study Center and other AE reports received from the Sponsor or designee, in accordance with local procedures.

The Investigator will be responsible for obtaining annual IEC/IRB approval/renewal throughout the duration of the study in accordance with local procedures.

